6. STUDY OBJECTIVES AND PURPOSE

6.1. Primary Objectives

[figure not shown]
The primary objective is to assess the long-term safety and tolerability of the OCA + BZF FDC tablet in subjects with PBC.

6.2. Efficacy Objectives

[figure not shown]
The efficacy objective is to assess the effects of the OCA + BZF FDC tablet in subjects with PBC on the following:

- Biochemical disease markers, including ALP, GGT, ALT, AST, and total and conjugated bilirubin
- ALP $<1.67\times$ ULN, total bilirubin \leq ULN, and ALP decrease of $\geq 15\%$ from baseline
- Noninvasive assessments of liver fibrosis (transient elastography [TE], enhanced liver fibrosis [ELF] score)
- Disease severity scores (GLOBE, UK-PBC, and model of end-stage liver disease [MELD])

6.3. Exploratory Objectives

- MELD score ≥ 15

7. INVESTIGATIONAL PLAN

7.1. Overall Study Design

7.1.1. Methodology

This Phase 3, open-label, LTSE study will evaluate the safety, tolerability, and efficacy of the OCA + BZF FDC tablet (OCA 5 mg + BZF 400 mg SR) in approximately 133 subjects with PBC for up to 60 months (5 years).

- For subjects from Study 747-213 or Study 747-214 who continue to meet that protocol's requirements, they will transition into Study 977-311 once the study is active at their respective sites. The time subjects have spent in the LTSE phases in their respective studies, 747-213 or 747-214, will not count toward the 60 months in Study 977-311.
- Eligible subjects from other Sponsor studies may also transition to Study 977-311.

[figure not shown]
All subjects will transition in Study 977-311 to the OCA + BZF FDC tablet (OCA 5 mg + BZF 400 mg SR) and will receive investigational product once daily at the same time (AM dosing is preferred to align with all study visits) starting on Day 2. All subjects should continue their prestudy dose of UDCA throughout study participation.

After the Day 1, Day 2, Month 1, Month 3, Month 6, and Month 12 visits, subsequent in-clinic study visits will occur every 6 months for the assessment of safety, tolerability, efficacy, PK, and PD.

The study design diagram is presented in Figure 1.

7.1.2. Study Design Diagram

Figure 1: Study Design Schematic

BZF=bezafibrate; D=day; EOS=end of study; FDC=fixed-dose combination; IP=investigational product; LTSE=long-term safety extension; M=month; OCA=obeticholic acid; SR=sustained release; UDCA=ursodeoxycholic acid

Notes: Subjects taking UDCA at the time of enrollment will remain on their stable dose of UDCA during the study.

Subjects will be re-consented.

Subjects in either Study 747-213 or Study 747-214 may already be in LTSE. The time subjects spent in LTSE on either study will not be carried over into this study, 977-311. Subjects will spend a total of 60 months (5 years) in Study 977-311.

^a The Day 2 Visit can be either a virtual or onsite visit. It will be scheduled on Day 2 to Day 7 of the study depending on when laboratory results are available and reviewed. Subjects can elect to pickup IP onsite (onsite Day 2 visit) or have it shipped directly to them (virtual Day 2 visit). For subjects that have IP shipped, the Day 2 virtual visit should be scheduled once the subject receives IP.

7.1.3. Schedule of Study Procedures**Table 3: Schedule of Study Procedures**

Study Visit	Day 1	Day 2 Visit (Day 2 to Day 7) ^a	M1	M3	M6	M12	Every 6 Months from M12	ET ^b	M60 (EOS)
Visit Window			±2 weeks	±2 weeks	±2 weeks	±2 weeks	±2 weeks	±1 week	±2 weeks
Fast ≥8 Hours Prior to Visit ^c	X		X	X	X	X	X	X	X
Informed Consent Form	X								
Inclusion/Exclusion Criteria	X	X ^d							
Concomitant Medications	X	X	X	X	X	X	X	X	X
Myopathy Evaluation and Monitoring ^e	X	X	X	X	X	X	X	X	X
Physical Examination	X		X	X	X	X	X	X	X
Height	X								
Weight (including BMI and waist-hip ratio) ^f	X		X	X	X	X	X	X	X
Vital Signs ^g	X		X	X	X	X	X	X	X
12-Lead ECG	X							X	X
AEs ^h	X	X	X	X	X	X	X	X	X
CP Assessment ⁱ	X		X	X	X	X	X	X	X
MELD Score ^j	X		X	X	X	X	X	X	X
MRS	X		X	X	X	X	X	X	X
GLOBE and UK-PBC ^l	X		X	X	X	X	X	X	X
Administer IP ^m		X ⁿ	X	X	X	X	X		
Dispense IP		X ^a	X	X	X	X	X		
Assess IP Accountability and Compliance		X ^o	X	X	X	X	X	X	X
Serum Chemistry, Hematology,	X		X	X	X	X	X	X	X

Study Visit	Day 1	Day 2 Visit (Day 2 to Day 7) ^a	M1	M3	M6	M12	Every 6 Months from M12	ET ^b	M60 (EOS)
Visit Window			±2 weeks	±2 weeks	±2 weeks	±2 weeks	±2 weeks	±1 week	±2 weeks
Coagulation ^p (including CK)									
Virology (HCV/HBsAg)	X								
Urinalysis	X		X	X	X	X	X	X	X
Urine-Based β-hCG Pregnancy Test ^d	X		X	X	X	X	X	X	X
TE ^r	X		X	X	X	X	X	X	X
ELF score	X		X	X	X	X			

AE=adverse event; [REDACTED]; β-hCG=Beta-human chorionic gonadotropin; BMI=body mass index; [REDACTED]; CP=Child-Pugh; CK=creatinine kinase; ECG=electrocardiogram; EDC=electronic data capture; eCRF=electronic case report form; eGFR=estimated glomerular filtration rate; ELF=enhanced liver fibrosis; EOS=end of study; ET=early termination; [REDACTED]; HBsAg=hepatitis B surface antigen; HCV=hepatitis C virus; IP=investigational product; M=month; MELD=model of end-stage liver disease; MRS=Mayo Risk Score; [REDACTED]; PK=pharmacokinetic; [REDACTED]; QOL=quality of life; TE=transient elastography; UDCA=ursodeoxycholic acid

Notes: Unscheduled visits should occur as needed in the event of signs or symptoms of suspected hepatic injury or decompensation or if laboratory alerts have been triggered. Subjects who discontinue investigational product but continue in the study may be requested to come in for an Unscheduled Visit at the discretion of the Investigator depending on the timing of their next scheduled study visit. Unscheduled visits are optional and should occur as needed based on Investigator discretion; a PK sample should be collected if an unscheduled visit occurs due to a safety event.

^a The Day 2 Visit can be either a virtual or onsite visit. It will be scheduled on Day 2 to Day 7 of the study depending on when laboratory results are available and reviewed. Subjects can elect to pickup IP onsite (onsite Day 2 visit) or have it shipped directly to them (virtual Day 2 visit). For subjects that have IP shipped, the Day 2 virtual visit should be scheduled once the subject receives IP.

^b An ET visit should occur in subjects who withdraw from the study. The ET visit should be completed as near as possible to the subject's last dose of IP. Study procedures and assessments are not required if previously completed within 4 weeks of the ET.

^c Subjects should be instructed to fast overnight (at least 8 hours) before all in-clinic study visits, but water is permitted. Record fasting status in the source and eCRF. If the subject reports having eaten or drunk anything other than water within 8 hours, document accordingly in the source and eCRF and remind the subject that fasting is required before all onsite study visits.

^d On the Day 2 Visit, the Investigator will review Day 1 eligibility laboratory results. If any laboratory results are out of range, the Medical Monitor and Sponsor Medical Monitor will review and determine an appropriate plan for the subject on a case-by-case basis.

^e If subjects develop myopathy at any point during the study, CK values must be checked. A CK $\geq 5 \times$ ULN or $\geq 3 \times$ ULN with symptoms consistent with rhabdomyolysis will require investigational product interruption. Laboratory values including CK and creatinine will be closely monitored every 2 weeks until values return to baseline levels.

^f Waist-to-hip ratio will be calculated via EDC from waist and hip circumference measurement.

^g Body temperature, sitting heart rate, respiratory rate, and seated blood pressure after sitting for 3 minutes.

^h AE data will be collected from the time that signed informed consent is obtained until the subject fully completes her/his participation in the study.

ⁱ CP Score will be calculated based on central laboratory evaluations and a targeted assessment of ascites and hepatic encephalopathy. Scores will be recorded on the eCRF.

^j MELD score will be calculated from serum chemistry and other parameters collected at the same visit. Scores will be recorded on the eCRF.

^l GLOBE and UK-PBC scores will be calculated from serum chemistry and other parameters and recorded on the eCRF.

^m At each study visit, the dose of investigational product should be administered daily at the same time (AM dosing is preferred to align with all study visits) starting on Day 2. All assessments must be completed before administration of investigational product and UDCA (if applicable).

ⁿ Subjects who have an onsite Day 2 visit will be administered investigational product onsite. Subjects who have a virtual Day 2 visit will self-administer investigational product during the virtual visit.

^o For subjects who have a virtual day 2 visits and have had IP shipped, the Investigator to confirm that IP was received in good condition, was untampered, and is the correct drug. Date of first IP administration should be recorded.

^p See analytes listed in [Table 11](#).

^q Urine-based β -hCG pregnancy tests must be performed in females of childbearing potential (defined in [Section 9.7.2.1](#)) prior to entry and at every visit. If positive, a confirmatory serum pregnancy (quantitative β -hCG) blood test must be performed at the central laboratory. If the confirmatory blood test is also positive, the subject may not continue in the study taking IP. (Additional testing may be conducted where required, regionally.)

^r To be performed only if test is available at qualified sites.

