The most commonly reported AE related to OCA is pruritus. Although pruritus has been observed in healthy volunteers and subjects with chronic liver disease, it most frequently occurs in subjects with PBC, which is not unexpected given that pruritus is a common symptom of chronic cholestatic diseases. In subjects with PBC, treatment with OCA at doses of 5, 10, 25, and 50 mg has been shown to cause a dose-dependent exacerbation of this common symptom. While the majority of pruritus events were mild and moderate in severity, severe pruritus was reported in 23% of subjects in the OCA 10 mg arm, 19% of subjects in the OCA titration arm, and 7% of subjects in the placebo arm in the pivotal Phase 3 study (747-301). In the subgroup of patients in the OCA titration arm who increased their dosage from 5 mg once daily to 10 mg once daily after 6 months of treatment (n=33), the incidence of severe pruritus was 0% from Months 0 to 6 and 15% from Months 6 to 12. The median time to onset of severe pruritus was 11 days, 158 days, and 75 days for patients in the OCA 10 mg, OCA titration, and placebo arms, respectively.

Lipid Profile Changes

Decreases in HDLc levels, which have been observed in subjects with PBC and MASH, were generally evident within 2 weeks of treatment commencement and trended back toward baseline with continued treatment. The clinical impact of the decrease in HDLc is unknown, especially for subjects with PBC in the context of their relative baseline elevated HDLc levels.

In subjects with PBC, a small but transient increase of LDLc levels was seen within 2 weeks of treatment commencement with OCA; however, mean LDLc levels in both OCA treatment arms in the pivotal Phase 3 study were almost identical with that observed in the placebo treatment arm by the end of the 52-week study. The clinical relevance of the treatment-emergent decrease in HDLc and modest and transient elevation in LDLc in this subject population is unknown and has not been shown to be associated with increased cardiovascular risk.

AE=adverse event; CCDS=Company Core Data Sheet; HDLc=high-density lipoprotein cholesterol; LDLc=low-density lipoprotein cholesterol; MASH=Metabolic dysfunction-associated steatohepatitis; OCA=obeticholic acid; PBC=primary biliary cholangitis; PEY=patient exposure years

Sources: CCDS (on file) and [OCA Investigator's Brochure](#)

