8.4.3. Subject Discontinuation Notification

The Investigator must notify the Sponsor as soon as possible if any subject prematurely discontinues from the study. The date when the subject is withdrawn and the primary reason(s)

for discontinuation must be recorded in the eCRF; additional information may be requested by the Sponsor to complete a discontinuation narrative.

If a subject is withdrawn from the study early (regardless of the cause), all of the early termination (ET) evaluations are to be performed at the time of withdrawal, to the extent possible.

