9.7.2. LTSE Period

[figure not shown]
Subjects from Study 747-213 or Study 747-214 (or other Sponsor studies) will transition into Study 977-311 once the study is active at their respective sites. The time subjects have spent in the LTSE phases in their respective parent studies will not count toward the 60 months in Study 977-311.

All subjects will transition in Study 977-311 to the OCA + BZF FDC tablet (OCA 5 mg + BZF 400 mg SR) and will receive investigational product once daily at the same time (AM dosing is preferred to align with all study visits) starting on Day 2. All subjects should continue their prestudy dose of UDCA throughout study participation.

9.7.2.1. Day 1

The following procedures will be performed as listed in [Table 3](#):

- Verify that the subject has fasted for at least 8 hours
 - Record fasting status in the source and eCRF
 - If the subject reports having drunk or eaten anything other than water within 8 hours, document accordingly in the source and eCRF and remind the subject that fasting is required before all onsite study visits
- Review ICFs and obtain signatures before performing any study-related procedures
- Verify inclusion and exclusion criteria for eligibility
- Record concomitant medications
- Assess and record any pretreatment AEs including myopathy evaluation (after the ICF has been signed)
- Perform physical examination
- Measure height and record weight and body mass index (BMI) and waist-to-hip ratio (WHR)
- Record vital signs (body temperature, sitting heart rate, respiratory rate, and seated blood pressure after sitting 3 minutes)
- Perform standard 12-lead electrocardiogram (ECG)
- Calculations will be performed for the following:
 - CP Score/Class (assessment of ascites and hepatic encephalopathy is required). See [Section 7.4.4](#) for additional information regarding CP scoring.
 - MELD Score: to be calculated from serum chemistry and other parameters
 - MRS
 - GLOBE and UK-PBC scores
- Obtain blood samples for the following:
 - Serum chemistry, hematology, and coagulation; see analytes listed in [Table 11](#).
 - Virology: HCV/HBsAg
 - A dedicated serum sample will be collected and sent to the vendor for laboratory testing and calculation of ELF score

- Urinalysis

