13.1. PK Blood Sampling

All PK blood collections must be performed at the clinical site and not at a local lab.

Subjects need to be in fasting condition for at least 8 hours prior to collection of PK samples. A [REDACTED] through Month 60 (EOS), and the ET and/or Unscheduled Visits (if applicable). A [REDACTED] also must be collected within 7 days of a safety event (e.g., event related to potential hepatic or muscular injury).

The acceptable windows for sample collection on Month 1 through Month 60 Visits are shown in Table 7. There is no window required for the Day 1 Visit as investigational product will not be administered.

Table 7: Acceptable Windows for Pharmacokinetic Sample Collection (Month 1 through Month 60)

Nominal Sampling Time	Acceptable Sampling Window
[REDACTED]	30 minutes ±15 minutes before dosing

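### The 4-week waiver at the early-termination visit has no post-dose condition, so pre-dose Day 1 labs and ECG can stand in for it, and it conflicts with Protocol Section 8.4.3

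*Protocol*

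**What the plan says.** **The waiver.** Protocol Section 7.1.3, Table 3, footnote b applies to subjects who withdraw from the study. It says "The ET visit should be completed as near as possible to the subject's last dose of IP", and then: "Study procedures and assessments are not required if previously completed within 4 weeks of the ET". Nothing limits this to assessments made after the first dose.

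**The competing instruction.** Section 8.4.3 says that when a subject is withdrawn early, whatever the cause, "all of the early termination (ET) evaluations are to be performed at the time of withdrawal, to the extent possible". It neither mentions the waiver nor refers to footnote b. Appendix B shows that the footnote and the ET wording of Section 8.4.3 both came in with protocol Version 2.0, so neither replaces the other.

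**What precedes dosing.** Section 13.1 confirms that Day 1 is before treatment: "There is no window required for the Day 1 Visit as investigational product will not be administered". The first dose is taken at the Day 2 Visit, and Section 7.1.2 says of that visit: "It will be scheduled on Day 2 to Day 7 of the study depending on when laboratory results are available and reviewed". In Table 3 the Day 2 Visit has no labs, vital signs, physical examination or ECG. The next visit with labs is Month 1, with a window of ±2 weeks. ECGs are scheduled only at Day 1, ET and Month 60.

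**How the data are used.** One dose places a subject in the LTSE Population, the primary safety population (Protocol Sections 15.1 and 15.3). Protocol Section 15.3.2 plans laboratory shift tables from Day 1 through Month 60 or ET. SAP Section 5.5 restricts analyses to scheduled visits and sends unscheduled results to listings. Protocol Section 15.7 assumes data missing completely at random, with no imputation.

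**The concern.** The ET visit is there to record the subject's state close to the last dose. If the Day 1 results can fill it, an early withdrawal contributes a pre-drug assessment in place of an on-drug one. Safety and tolerability are the primary objective, and subjects who leave in the first weeks are those in whom early intolerance is most likely to show.

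The ECG is the clearest case. For anyone who withdraws, the ET tracing is the only on-drug ECG that the schedule provides. In the first four weeks it can be waived on the strength of the pre-dose tracing, even when Month 1 was attended.

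Sites also have two instructions that can be read in opposite ways, so practice may differ between about 60 centres.

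**Working it through.** The plan states no figure on this point, so there is nothing to reproduce. The check uses calendar arithmetic on the protocol's own visit days, followed by a scale calculation on an assumed withdrawal rate.

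**1. Reach of the Day 1 waiver.**
- Day 1 + 28 days = Day 29, the last ET day that Day 1 results can cover.
- First dose on Day 2: 29 − 2 + 1 = 28 days on drug at most.
- First dose on Day 7: 29 − 7 + 1 = 23 days on drug at most.

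**2. When Month 1 can supply on-drug values.** Taking Month 1 as nominal Day 29 to 31, the −2 week window opens at about Day 15 to 17.

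| ET falls on | Labs, vital signs, physical examination | ECG |
|---|---|---|
| First dose to about Day 15–17 | Only Day 1 values exist from scheduled visits; they can count as ET | Day 1 tracing can count as ET |
| About Day 15–17 to Day 29 | Day 1 values can be the only ones if Month 1 has not been done | Day 1 tracing can count as ET, whether or not Month 1 was done |
| After Day 29 | Day 1 values no longer qualify | Day 1 tracing no longer qualifies; ET ECG is due |

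**3. How many subjects.** The documents give no withdrawal rate, so this is an assumption shown as a range. With a 60-month withdrawal proportion d at constant hazard and 60 months taken as about 1826 days, the expected number withdrawing in the first 28 days is 133 × [1 − (1 − d)^(28/1826)].

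| d over 60 months | Probability by 28 days | Expected of 133 |
|---|---|---|
| 10% | 0.00161 | 0.2 |
| 20% | 0.00342 | 0.5 |
| 30% | 0.00545 | 0.7 |
| 50% | 0.01057 | 1.4 |

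Constant hazard may understate early withdrawal after a change of regimen. If 1% to 5% leave in the first four weeks, the number is 133 × 0.01 = 1.3 to 133 × 0.05 = 6.7, or about 1 to 7.

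**4. Later in the study.** Twelve visits (Day 1, M1, M3, M6, M12, and M18 to M54 every 6 months) each open a 28-day waiver: 12 × 28 = 336 days, and 336/1826 = 18.4%. This is the share of calendar time in which labs and other non-ECG items can be waived. No ECG is scheduled from M1 to M54, so for the ECG only the Day 1 window counts: 28/1826 = 1.5%.

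**The case against.** **Several provisions narrow the gap, and they stand.** Footnote b concerns withdrawal from the study. Subjects who only stop the drug are asked to keep attending visits (Protocol Sections 7.6, 8.4 and 8.4.1.1), so their Month 1 labs remain due. Hepatic symptoms call for liver biochemistry (Sections 7.4.1 and 7.4.2), and muscle symptoms call for a CK (footnote e and Section 7.4.4.3), independently of ET. Sites may also do more than footnote b requires. But labs triggered by symptoms would usually be unscheduled, and SAP Section 5.5 keeps those out of the summaries.

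**The two passages might be read together.** Table 3 with its footnote could be taken to define what the ET evaluations are, and Section 8.4.3 as saying when to do them. That reading is possible, but the text does not state it. The feasibility qualifier in Section 8.4.3 does not obviously allow an older result to serve. Even on this reading, the pre-dose problem in footnote b remains.

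**Three stronger readings are tempting, and the documents do not support them.**
- A reader might infer that an early withdrawal leaves no on-drug safety data at all. AEs are collected from consent to the end of participation, and SAEs for 30 days after study discontinuation (Sections 14.1.4.1 and 14.1.8). IP accountability is also an ET item that is not done on Day 1.
- A reader might take 18% as the share of withdrawals needing no ET procedures. The ECG remains due at ET after about Day 29 unless an unscheduled one was done, and calendar time equals a share of withdrawals only if these are evenly spread.
- A reader might point to Section 5.6.2, "The median time to onset of severe pruritus was 11 days, 158 days, and 75 days", as showing that severe pruritus falls inside the window. The 11 days belong to OCA 10 mg in another study. Here subjects roll over while already taking investigational product, the tablet contains OCA 5 mg, and pruritus is captured as an AE.

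**The effect on percentages is not settled.** SAP Sections 5 and 5.3 use non-missing denominators, while Appendix A uses the analysis population. Under the first, the subject leaves the denominator; under the second, the subject stays in it without a post-baseline value.

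**Conclusion.** The point holds within limits. On its literal wording, footnote b lets the pre-dose Day 1 ECG count as ET for a dosed subject who withdraws by about Day 29. Before Month 1 is done, it lets the Day 1 labs, vital signs and physical examination count as well. What is lost is the on-drug value of these assessments in the scheduled-visit summaries; AE and SAE reporting is not affected. Footnote b and Section 8.4.3 also need to be reconciled, because a site cannot tell which one governs.

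The group is probably small, between a fraction of one subject and about 7 of 133. That range rests entirely on assumed withdrawal rates. After Day 29, results from later visits that stand in under the waiver were obtained after treatment had started (for subjects still on treatment, on drug), so a 4-week allowance there is an ordinary saving of burden, though a result may precede the event that led to withdrawal. This is a modest defect that is cheap to correct in a study whose primary objective is safety.

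**What to change.** - Add one sentence to Table 3 footnote b: assessments performed before the first FDC dose in Study 977-311 do not count toward the ET visit.
- In Section 8.4.3, refer to footnote b and say whether the waiver applies, so that the two passages give one instruction.

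The cost is an edit in two places and, for a few early withdrawals, a repeat blood draw, examination or ECG at a visit the schedule already asks for. The analysis plan needs no change for this.
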